PERFORM STUDY

A POST MARKET OBSERVATIONAL STUDY ON THE USE OF CORMATRIX[®] ECM[®] FOR FEMORAL ARTERIAL RECONSTRUCTION

STUDY SPONSOR: CorMatrix Cardiovascular, Inc. [name]

PROTOCOL NUMBER: 14-PR-1120 REVISION: C

January 11, 2016

Please Note: Confidential information contained herein is made available to you in your capacity as Investigator, Medical Advisor, or Consultant to CorMatrix Cardiovascular, Inc. ("CorMatrix"). It is provided only for review by you, your staff, IRB/Ethics Committee members, or other regulatory authority. Except as necessary to obtain properly informed consent for participation, it is expected that there will be no disclosure to other persons.

Investigator Statement of Compliance

I hereby agree to comply with this protocol and applicable regulations governing clinical trials, including local regulations, and Good Clinical Practice / ICH Guidelines.

Investigator Signature:

Date:

Table of Contents –

TAB	BLE OF CONTENTS –	2
STU	DY COORDINATION	3
1.	INTRODUCTION AND RATIONALE	5
2.	INDICATION FOR USE	5
3.	DESCRIPTION	5
4.	PRIOR CLINICAL EVALUATIONS	6
5.	STUDY OBJECTIVES	7
6.	STUDY DESIGN	7
7.	STUDY POPULATION	7
8.	STUDY PROCEDURES	8
9.	ADVERSE EVENT REPORTING	9
10.	DATA ANALYSIS	12
11.	ETHICAL CONSIDERATIONS	12
12.	BIBLIOGRAPHY	14
APP	ENDIX A: SAMPLE INFORMED CONSENT/PATIENT INFORMATION SHEET	17
APP	ENDIX B: CASE REPORT FORMS	18
APP	ENDIX C: INSTRUCTIONS FOR USE	19
APP	ENDIX D: SPONSOR COMMITMENTS	20
APP	ENDIX E: INVESTIGATOR QUALIFICATIONS AND RESPONSIBILITIES	21

CorMatrix Cardiovascular, Inc.

STUDY COORDINATION

STUDY SPONSOR CORMATRIX CARDIOVASCULAR, INC. [name]

DATA COORDINATIONCORMATRIX CARDIOVASCULAR, INC.CENTER1100 OLD ELLIS ROADROSWELL, GA 30076

Study Synopsis

OBJECTIVE	The objective of the study is to actively gather additional information on				
	the use of CorMatrix ECM for vascular repair in the reconstruction of				
	the femoral artery.				
STUDY	Up to 5 clinical sites will enroll up to 100 subjects who have received				
POPULATION	CorMatrix ECM for vascular repair.				
INDICATIONS FOR	he CorMatrix® ECM® for Vascular Repair is intended for use as a				
USE	patch material for repair and reconstruction of peripheral vasculature				
	including the carotid, renal, iliac, femoral, and tibial blood vessels. The				
	CorMatrix ECM for Vascular Repair may be used for patch closure of				
	vessels, as a pledget, or for suture line buttressing when repairing				
	peripheral vessels.				
ENDPOINTS	The endpoint is defined as the proportion of subjects with device related				
	adverse events.				
EXAMINATION	The examination schedule is as follows: Pretreatment/treatment, four to				
SCHEDULE	six weeks, six months and twelve months following femoral arterial				
	reconstruction with the CorMatrix ECM for vascular repair.				
CLINICAL	The following clinical assessments will be performed:				
PARAMETERS	Assess medical history at baseline				
	• Assess medications at baseline and for changes at all				
	follow up visits				
	• Device related adverse event assessment at treatment, 4-6				
	weeks, 6 months and 12 months				
	• Duplex imaging at 4-6 weeks, 6 months and 12 months				

1. Introduction and Rationale

Atherosclerosis and thrombosis are the main pathological processes involved in ischemic stroke, coronary heart disease and peripheral arterial disease. The disease prevalence of systemic atherosclerosis is approximately 3% to 10%, increasing to 20% in persons aged 70 years and older. Femoral endarterectomy with patch angioplasty has been the favored approach to the treatment of patients with symptomatic common femoral artery (CFA) occlusive disease. Primary patency rates of 74% to 91% at 5 years have been reported in the literature.

The development of carotid patches, as well as patches for use in arteriotomy closure elsewhere, continues to remain a critical adjunct for vascular surgery. The CorMatrix ECM for vascular repair is an attractive vascular patch material due to its ability to be remodeled into healthy native tissue.

The CorMatrix ECM for Vascular Repair acts as a decellularized scaffold for use as a vascular patch to repair the peripheral vessels. The extracellular matrix (ECM) scaffold is a biomaterial derived from porcine small intestinal submucosa (SIS). The SIS is developed from a select layer of tissue that is recovered from porcine small intestine. The decellularized ECM scaffold allows the patient's own cells to migrate and attach within the ECM to naturally repair the tissue defect.

CorMatrix Cardiovascular, Inc. received FDA 510(k) premarket clearance for the CorMatrix ECM for Vascular Repair on July 16, 2014. This Phase IV, post market observational study, will evaluate the safety and effectiveness of CorMatrix ECM for femoral arterial reconstruction by collecting specific data at pretreatment, treatment, 4-6 weeks, 6 months and 12 months following femoral arterial reconstruction with the CorMatrix ECM for vascular repair. Data collected from this study will not be used to support a marketing claim or change in labeling. This study is being performed to gather post-market data only and is not being performed under the direction of the FDA.

2. Indication for Use

The CorMatrix® ECM® for Vascular Repair is intended for use as a patch material for repair and reconstruction of peripheral vasculature including the carotid, renal, iliac, femoral, and tibial blood vessels. The CorMatrix ECM for Vascular Repair may be used for patch closure of vessels, as a pledget, or for suture line buttressing when repairing peripheral vessels. The entire Instructions for Use can be found in Appendix C.

3. Description

The CorMatrix® ECM® for Vascular Repair is intended for use as a patch material for repair and reconstruction of peripheral vasculature including the carotid, renal, iliac, femoral, and

tibial blood vessels. The CorMatrix ECM for Vascular Repair may be used for patch closure of vessels, as a pledget, or for suture line buttressing when repairing peripheral vessels.

The CorMatrix ECM for Vascular Repair is an extracellular matrix (ECM) scaffold derived from porcine small intestinal submucosa (SIS). The device is constructed of a multilaminate (6-ply), decellularized, non-crosslinked, lyophilized ECM cut to specific shapes and sizes and terminally sterilized using Ethylene Oxide gas. The CorMatrix ECM for Vascular Repair will be supplied as a 6-ply, lyophilized, sterilized sheet of SIS-ECM.

4. Prior Clinical Evaluations

CorMatrix ECM has been studied in previous prospective clinical evaluation, and a postmarket clinical study is ongoing. The ECM for Pericardial closure has been studied in a randomized, prospective study to evaluate its ability to reduce the incidence of new onset atrial fibrillation; the ECM for Carotid Repair is under evaluation in a post-market study to capture and assess device performance data from subjects undergoing patch angioplasty of the carotid artery following carotid endarterectomy using the product per its FDA-cleared Indications for Use.

4.1 Post-market Clinical Evaluation of the ECM for Carotid Repair

CorMatrix is currently conducting a post-market registry study for the CorMatrix ECM for Carotid Repair (Protocol No. 11-PR-1021). The objective of this registry is to capture and assess device performance data from subjects undergoing patch angioplasty of the carotid artery following carotid endarterectomy using the CorMatrix ECM for Carotid Repair per its commercial Indications for Use. This registry provides an ongoing post-market surveillance mechanism to document clinical outcomes on the use of the CorMatrix ECM for Carotid Repair. This is a multi-center, prospective, single-arm, post-market, observational registry of subjects receiving the CorMatrix ECM for Carotid Repair for patch angioplasty following carotid endarterectomy procedures. This post-market registry may involve up to ten U.S. clinical sites and up to 230 subjects. Data will be collected through the 24-month follow-up.

One-hundred and eighty six patients are enrolled in the study and included in the interim analysis of the CorMatrix ECM for Carotid Repair registry. The data demonstrated that the rate of device related adverse events were consistent with the rates found in the review of the contemporary literature for patch angioplasty. Specifically, no unanticipated events were found and the rate of the events was as anticipated in the risk management plan. Of specific interest in the analysis was the rate of pseudoaneurysm, which was present in 2 (1.08%) of the 186 patients and compared favorably to the rates found in the literature (1.4% to 5%).

The mean carotid stenosis (maximum) at pre-operative was 85.5%. Mean change from baseline values were -52.5%, -53.9%, -58.4%, and -45.2% at the 1- to 3-month, 6-month, 12-month, and 24-month follow-up evaluations. The mean carotid stenosis (minimum) at pre-operative was 72.5%. Mean change from baseline values were -64.5%, -63.7%, -

63.2%, and -60.4% at the 1- to 3-month, 6-month, 12-month, and 24-month follow-up evaluations.

As a result of this analysis and the directed and ongoing risk management activities, the overall residual risk of the CorMatrix ECM for Carotid Repair is determined to be acceptable.

5. Study Objectives

The objective of the study is to actively gather additional information on the use of CorMatrix ECM for vascular repair in the reconstruction of the femoral artery.

Endpoint

The endpoint is defined as the proportion of subjects with device related adverse events.

6. Study Design

This is a multi-center, Phase IV, prospective, single arm, post-market observational study of subjects undergoing femoral arterial reconstruction using the CorMatrix ECM for vascular repair per its FDA cleared Indications for Use. It is anticipated that up to 5 eligible sites will participate enrolling up to 100 subjects. Eligible candidates will be approached to ascertain interest in study participation. The approved Informed Consent and/or Patient Information Sheet will be completed and the process will be documented in the subject study binder by the research staff. Patients who have undergone a femoral arterial reconstruction using the CorMatrix ECM will be followed as per their usual standard of care. Information will be collected at follow up visits 4-6 weeks, 6 months and 12 months.

7. Study Population

Subjects are considered to be enrolled into this study at the completion of their surgical procedure of femoral arterial reconstruction with the use of CorMatrix ECM. Before any subject can be enrolled, the IRB for the specific institution must approve the protocol and the Informed Consent/Patient Information Sheet.

Subjects must meet the following requirements to be eligible for enrollment in this study:

Inclusion Criteria:

- Subjects must be undergoing femoral arterial reconstruction with patch angioplasty closure.
- Subject's surgeon intends to use CorMatrix ECM as the patch material for femoral arterial reconstruction per its FDA cleared Indications for Use.
- The subject must possess the ability to provide informed consent.
- The subject must express an understanding and willingness to fulfill all of the expected requirements of this protocol.

Exclusion Criteria:

• Known sensitivities to porcine material

8. Study Procedures

Study procedures are standardized to the extent possible and explained in detail below and are summarized in Table I - Study Procedure Overview.

All study-related data will be captured on standardized Case Report Forms. A copy of the Case Report Forms is provided in Appendix B. Case report forms will be sent to CorMatrix via fax at [contact] (attention [name]) or via scan/email to [contact]

Activity	Pre-Tx	Treatment	Week 4-6	Month 6	Month 12
Assess Eligibility	Х				
Informed Consent Process	Х				
Medical History/update	Х	X	Х	Х	Х
Medication history/update	Х	X	Х	Х	Х
Duplex Imaging	X*		Х	Х	Х
Surgical Complications		X			
Assessment for Adverse		X	Х	X	X
Events					
Infection Information		X	X	X	X

 Table 1: Study Procedure Overview

*Data captured if performed, not required

8.1 Pre-Treatment Procedure

Patients presenting for femoral arterial reconstruction with patch angioplasty will be screened for study eligibility. Eligible candidates will be approached to ascertain interest in study participation. Before any study specific tests are performed, the patient will have the details of the study fully explained and will sign an approved Informed Consent or, if Waiver of Documentation of Consent, patient will verbalize understanding. The consent process will be documented by research personnel and the patient will be provided with a copy of the Informed Consent and/or Patient Information Sheet.

A pretreatment visit will be conducted prior to surgery and for all subjects:

- Documentation of the consent process
- Demographic information
- Medical history, including indication for surgery
- Duplex Imaging, if performed
- Relevant medications

8.2 Treatment Procedure

The subject will undergo a standard femoral arterial interventional procedure. The subject's femoral arteriotomy will be closed using the CorMatrix ECM for arterial repair. The Investigator will implant the CorMatrix ECM according to the FDA cleared Instruction for Use and per the surgeon's standard of care. Specific data on the procedure as well as the CorMatrix ECM will be collected. Device related adverse events will be documented on the case report form.

8.3 Post-operative

The Investigator's standard post-operative procedures will be followed. Post-operative data from the end of the procedure until the subject is discharged from the hospital will be collected and includes length of hospital stay, medications upon discharge and any complications/adverse events.

8.4 Follow up

Follow up assessments will be conducted at the 4-6 Week, 6 Month and 12 Month follow up visit per Table I - Study Procedure Overview. Data will be collected on the appropriate case report form.

9. Adverse Event Reporting

9.1 Definitions

Adverse Event (AE)

An adverse event (AE) will be defined as any undesirable clinical occurrence in a subject whether it is considered to be device related or not, that includes a clinical sign, symptom, or condition/observation of an unintended technical performance or performance outcome of the device. Causality is defined as not-related, possibly-related and probably-related to the device, which is further defined in Table 2: Event Relationship Assessment.

Serious Adverse Event (SAE)

A serious adverse event ("SAE") will be defined as an event that: 1) threatens life, 2) results in permanent impairment of a body function or permanent damage to a body structure, 3) necessitates medical or surgical intervention to preclude such impairment, 4) requires or prolongs hospitalization, or 5) is fatal (death).

Adverse Device Event

An Adverse Device Event will be defined as a clinical sign, symptom, or condition that is causally related to the device procedure, the presence of the device, or the performance of the device. Due to the temporal proximity of the AE to product administration, there is a reasonable possibility that the product may have caused the AE or may have contributed to the severity or duration of an event caused by other means.

AE Relationship	Description			
Not-related	A temporal relationship to the use of the product, which makes a			
	causal relationship clearly and incontrovertibly due to extraneous			
	causes, such as other drugs, products, chemicals, underlying			
	diseases, environment, etc. Not-related to the use of the product.			
Possibly-related	Occurring within a reasonable period of time relative to the use of			
	the product, which makes a causal relationship possible, but			
	plausible explanations may also be provided by other causes,			
	such as other drugs, products, chemicals, underlying disease,			
	environment, etc. Possibly-related to the use of the product.			
Probably-related	Occurring within a reasonable period of time relative to use of			
	product, which makes a causal relationship probable where the			
	relationship cannot be attributed to other causes, such as drugs,			
	products, chemicals, underlying disease, environment, etc.			
	Probably-related to the use of the product.			

Table 2: Event Relationship

9.2 Assessing and Recording Adverse Events

Each AE recorded must be documented on the Case Report Form. All serious and device related events must be reported immediately to CorMatrix via telephone or email within 24 hours of the Investigator becoming aware of the event. The case report form will be submitted to CorMatrix. The site will be contacted by CorMatrix for additional information including, but not limited to:

- Description of the event and underlying cause (diagnosis), coexisting disease, or other. In order to avoid vague, ambiguous, or colloquial expressions, the AE should be recorded in standard medical terminology rather than the subject's own words when possible.
- Date of onset and date of resolution. If the event is present at the Month 12 follow-up visit it will be marked as not resolved at study exit.
- Intensity of the event: mild, moderate, or severe.
- Frequency of the event: single episode, intermittent, or continuous.
- Action taken: none, medication, procedure, medication and procedure, or other.
- Relationship to the study treatment: not-related, possibly-related, or probably-related.

Any subject withdrawn from the study due to an AE will be followed until the outcome of the event is determined. The Investigator must ensure that the details of the event are documented in the medical notes including full details of the outcome, in addition to recording the event on the appropriate case report form.

All femoral procedure and device related serious adverse events that are associated with the use of the device will be evaluated in accordance with the protocol and the Sponsor's Incident/Event Reporting SOP. Any serious adverse event that requires a Medical Device Report will be reported by the Sponsor to the FDA in accordance with Sponsor's Medical Device Reporting SOP. The site should contact:

> [name] Project Administrator, CorMatrix [contact] (direct) [contact] (company) [contact]

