9.3 Possible Adverse Events

The following possible adverse events have been identified as possible risks from the CorMatrix ECM:

- Acute or chronic inflammation (Initial application of the CorMatrix ECM may be associated with transient, mild, localized inflammation.)
- Allergic reaction
- Bleeding
- Embolization of ECM
- Infection (superficial or deep)
- Patch dehiscence
- Pseudoaneurysm
- Recurrent stenosis
- Stroke
- Thrombosis
- Vessel occlusion

The following possible adverse events have been identified as possible risks from the surgical procedure:

- Reactions to anesthesia
- Bleeding
- Infection
- Nerve damage (skin numbness)
- Blood clots
- Hematoma
- Leg swelling
- Re-stenosis

This study will capture events reported at treatment, post-operatively, 4-6 Weeks, 6 months and 12 months follow up and as reported by the PI and/or subject and from a review of medical records.

10. Data Analysis

Since this is a Phase IV, post-market study, analyses will consist of tabulated data and descriptive statistics. Subject data listings and tabular and graphical presentations of the summary and statistical results will be provided. At a minimum, an interim report will be completed after 50 subjects have completed their four to six week follow-up. A final report will be completed at the end of the study. Additional quantitative and qualitative comparisons will be made to contemporary literature and similar studies.

11. Ethical Considerations

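### The only defined rate counts attributed events; also tabulate each device-list event regardless of attribution, and use those figures for literature comparisons

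*Combined protocol and SAP*

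**What the plan says.** - **Endpoint.** Section 5, repeated in the synopsis: "The endpoint is defined as the proportion of subjects with device related adverse events". The plan defines no other rate.
- **Design.** Section 6 describes a "prospective, single arm, post-market observational study" in which "up to 5 eligible sites will participate enrolling up to 100 subjects". The study coordination page names the manufacturer as both sponsor and data coordination center.
- **Rating.** Under Section 9.2 each adverse event goes on the case report form, and "All serious and device related events must be reported immediately to CorMatrix via telephone or email within 24 hours". The form is then submitted, and "The site will be contacted by CorMatrix for additional information including, but not limited to" a list that contains "Relationship to the study treatment: not-related, possibly-related, or probably-related".
- **Event lists.** Section 9.3 gives 11 possible risks of the device and 8 of the surgical procedure. Bleeding and infection are on both lists. Recurrent stenosis and thrombosis on the device list have near-equivalents (re-stenosis, blood clots) on the procedure list.
- **Scope of capture.** The synopsis and Section 8.2 speak only of device related events. Sections 8.3, 9.1 and 9.2 and Table 1 cover adverse events in general.
- **Comparison.** Section 10 is descriptive and adds: "Additional quantitative and qualitative comparisons will be made to contemporary literature and similar studies". Section 4.1, on the same sponsor's carotid registry, reports: "The data demonstrated that the rate of device related adverse events were consistent with the rates found in the review of the contemporary literature".

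**The concern.** Whether a patient counts in the only defined result depends on a causal judgement as well as on what happened. The site making that judgement knows which device was used, has no control group to compare with, and may be asked about the rating by the manufacturer. For the events on both Section 9.3 lists, choosing between device and procedure will often be a matter of opinion.

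This would matter less if the result were only described. Section 10, however, plans quantitative comparison with the literature, and Section 4.1 shows that the sponsor has already set device related rates beside published patch-angioplasty rates. If the published figure counts every occurrence and the study figure counts only attributed events, the two measure different things, and the mismatch runs one way. A reader of the final report could take a difference in definition for a difference in safety.

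**Working it through.** **1. The plan's own comparison.** Section 4.1 reports pseudoaneurysm in 2 of 186 carotid patients: 2/186 = 1.075%, which matches the stated 1.08%. It is set beside a literature range of 1.4% to 5%. The documents give no expected rate, margin or benchmark for the present endpoint, so there is no design figure to reproduce.

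**2. Direction of the mismatch.** For one event type among N subjects, let E be the number with the event and A the number with that event rated device related. Every subject in A is also in E, so A ≤ E. Let L be a literature rate that counts all occurrences. Then

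A/N − L = (E/N − L) − (E − A)/N.

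The last term is never negative. Using A in place of E therefore leaves the comparison unchanged or moves it in the device's favour. This assumes that L is an occurrence rate; the documents do not say how the literature counted.

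**3. Where E and A can part.** Four of the 11 device-list items (bleeding, infection, recurrent stenosis, thrombosis) have a same or similar entry on the procedure list. For these, E − A rests on judgement.

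**4. Size.** One subject whose only related event is rated not-related moves the endpoint by 1/100 = 1 percentage point at the maximum enrolment. With 50 subjects, the number that triggers the interim report, it is 1/50 = 2 points.

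As an illustration with assumed values, let p be the proportion of subjects with the event and q the share of them with no event rated related. The attributed rate is p × (1 − q):

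| p | q = 10% | q = 20% | q = 30% | q = 50% |
|---|---|---|---|---|
| 5% | 4.5% | 4.0% | 3.5% | 2.5% |
| 10% | 9% | 8% | 7% | 5% |
| 15% | 13.5% | 12% | 10.5% | 7.5% |

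Exact 95% intervals are 4.9% to 17.6% for 10/100 and 3.5% to 15.2% for 8/100. A fall from 10 to 8 subjects lies well inside sampling error, but it would be systematic, and the interval does not reveal it.

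**5. Can E be computed?** Under Sections 9.1 and 9.2 and Table 1, yes, because all adverse events are recorded. Under the synopsis and Section 8.2, read literally, not fully: an event judged unrelated need not be recorded at treatment (Section 8.2) or assessed at any visit (synopsis). The occurrence table therefore depends on reconciling these passages.

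**The case against.** The strongest reply is that the plan already holds what is needed. Adverse events are defined whatever their cause, listings and tabulations are promised, and occurrence counts could be produced at any time. Section 10 does not say that the attributed endpoint is the figure to be compared. The pseudoaneurysm example in Section 4.1 reads as a plain occurrence rate, so it may be like for like. The Adverse Device Event definition in Section 9.1 also reaches events caused by the device procedure, which would narrow the gap. The analysis is descriptive, and Section 1 rules out use for a marketing claim or labeling change.

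Much of this stands, and it limits the weight of the point. It does not remove it. The attributed proportion is the only rate the plan defines, Section 4.1 describes its general comparison in terms of device related events, and the endpoint is not tied to the Adverse Device Event term. That occurrence counts could be produced does not commit anyone to producing them.

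A reader might go further and infer that the sponsor obtains the rating by contacting the site, so that ratings will drift toward not-related. The documents do not support that:

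- Section 9.2 speaks of additional information. For a non-serious event, the 24-hour report already requires a site judgement of relatedness.
- Appendix E has the investigator sign and date the forms, with corrections lined out, dated and initialled, so changes on a form are traceable.
- Table 2 reserves not-related for events with an unmistakable outside cause, which works against downgrading. A query could also raise a rating.
- The case report forms are a separate document, so the absence of a relatedness field cannot be shown.

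**Conclusion.** The point holds as a modest, inexpensive improvement. The plan's only defined rate is filtered by an unblinded causal judgement that the manufacturer may query, and the plan intends comparison with published rates. Where those published rates count all occurrences (an assumption), the mismatch can only favour the device. Its size cannot be derived from the documents. What can be stated is 1 percentage point per subject at 100 subjects, for a subject with no other related event.

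A reader might take the 1.4% to 5% range in Section 4.1 as a yardstick for how few re-rated subjects would matter. It is not one: it refers to pseudoaneurysm alone, in the carotid setting, whereas this endpoint covers any device related event after femoral repair. Nor do the documents justify a rule that ratings may be raised but never lowered, since that would block legitimate corrections. Section 9.2 does not say whose rating is final or how disagreement is settled, but naming the rating used for the endpoint is at most a minor clarification.

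**What to change.** 1. In Section 10, beside the attributed endpoint, add a table of the number and proportion of subjects with each event on the Section 9.3 device list, regardless of attribution. State that these figures will be used wherever the literature rate is an occurrence rate.
2. Reconcile the synopsis and Section 8.2 with Sections 9.1 and 9.2 and Table 1, so that all adverse events are captured at treatment and at every follow-up visit.
3. Optionally, add one sentence naming the relatedness rating that enters the endpoint.

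The cost is a few lines of protocol text and one more table, with no adjudicator or added visit. The occurrence figures may look less favourable than the attributed rate and will include events due to the procedure or underlying disease. Both should therefore be shown and labelled.
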